8 Weeks Post-Quit (Visit 7). Participants will complete self-report questionnaires on a laptop computer; and expired CO and weight will be measured in a private room to ensure confidentiality. Participants will receive a \$40 payment for completion of the in-person assessments, which will take approximately 30 minutes to complete. Participants randomized to the CM treatment will receive an additional \$50 payment if they self-report abstinence from smoking over the past 7 days and have an expired CO level of ≤ 6 ppm. Participants who do not attend will be contacted by phone to obtain their self-reported smoking status.

12 Weeks Post-Quit (Visit 8). Participants will complete self-report questionnaires on a laptop computer; and expired CO and weight will be measured in a private room to ensure confidentiality. Participants will receive a \$40 payment for completion of the in-person assessments, which will take approximately 30 minutes to complete. Participants randomized to the CM treatment will receive an additional \$50 payment if they self-report abstinence from smoking over the past 7 days and have an expired CO level of ≤ 6 ppm. Participants who do not attend will be contacted by phone to obtain their self-reported smoking status.

26 Weeks Post-Quit (Visit 9; Follow-Up). Participants will complete self-report questionnaires on a laptop computer; and expired CO and weight will be measured in a private room to ensure confidentiality. Participants will receive a \$40 payment for completion of the in-person assessments, which will take approximately 40 minutes to complete. Saliva cotinine will also be measured via NicAlert test strips to provide additional evidence of abstinence. Participants who do not attend will be contacted by phone to obtain their self-reported smoking status and mailed a saliva cotinine test with instructions on how to complete the test.

Remote Treatment Follow-up Visits. Due to the evolving circumstances regarding COVID-19, participants will complete each follow-up visit remotely. The requirements and compensation for remote visits will be identical to in-person visits. Participants will remotely complete web-based questionnaires and provide a smartphone-based CO measurement using a Smokerlyzer iCO monitor. Participants randomized to the CM treatment will receive incentives in accordance with each visit given they meet the cessation requirements outlined above.

MEASURES

Biological/Anthropometric Measures.

[figure not shown]

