Expired Carbon Monoxide (CO) levels will be measured with a portable Vitalograph ecolyzer. CO levels of ≥ 8 -10 parts per million (ppm) suggest recent cigarette smoking with a sensitivity and specificity of approximately 90 percent. Thus, individuals will be eligible to participate in the current study if they produce CO levels ≥ 8 ppm at the screening visit. Conversely, abstinence from smoking will be verified with a CO level of < 10 on the quit day, and ≤ 6 ppm at all subsequent post-quit visits.

Saliva Cotinine will be measured with Accutest NicAlert test strips at the final follow-up visit (26 weeks post-quit). Cotinine levels of < 10 ng/ml suggest abstinence from smoking, while levels of 10 ng/ml or greater are consistent with smoking. Cotinine levels will be recorded by research staff as it becomes available on the test strip. After the result is recorded, test strips and saliva will be immediately discarded in a biohazard container.

Body Mass Index (BMI) will be calculated (kg/m^2) based on height measurements collected at visit 1 and weight measurements collected at each visit.

Traditional Questionnaire Measures.

Questionnaire data will be collected primarily on laptop computers. The amount of time needed to complete the computer-administered questionnaires varies by study visit. It is estimated that the longest visit (baseline) will require 1 hour to complete. We have found that even individuals with no experience

using computers have had few problems completing study assessments. We will include measures that are consistent with our working conceptual model (Figure 1). See Appendix A for assessment schedule and questionnaire measures.

Ecological Momentary Assessment. Participants will be trained in the EMA procedures at the baseline (1 week pre-quit) visit. Assessment items were selected based on their hypothesized relations to smoking behavior, temptation and lapse episodes, and/or their potential importance in understanding the influence of socioeconomic disadvantage. The items will assess smoking urges, affect, expectancies, self-efficacy, and related constructs. EMA items are detailed in the Appendix B.

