Aim 1. The sample size calculation ($N = 320$) assumes a 30% drop-out rate for both treatment arms. The number of subjects who will complete the 26-week trial ($n = 112$ in each group) was estimated based on the following assumptions: 1) SC abstinence rate is 10% at 26-weeks post-quit, 2) CM abstinence rate is 22% at 26 weeks post-quit; 3) equal allocation of subjects between two treatments; 4) type I error rate is set as 0.05; and 5) the targeted minimum power is 0.8. Logistic regression analyses will be conducted to evaluate the influence of adjunctive CM relative to SC on long-term smoking cessation (binary variable) outcomes at 26 weeks post-quit. The impact of treatment group on smoking cessation at secondary endpoints including the quit day, and at 1, 2, 3, 4, 8, and 12 weeks will also be evaluated. Generalized linear mixed models may also be used to evaluate the influence of treatment group on smoking cessation as a repeated outcome measure (see analysis plan in Aim 2). Covariates may include age, gender, race/ethnicity, nicotine dependence, and pharmacological treatment. As is the standard in smoking cessation intervention research, a conservative intention-to-treat approach will be employed in the primary analyses, such that participants with missing data or who have dropped out of treatment will be considered non-abstinent. Less conservative “completer” analyses will also be conducted where only participants with complete smoking status data will be included (i.e., those with missing data will be excluded).

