- Sources of Research Material.** Demographic, psychosocial, environmental and behavioral data will be collected via 1) traditional self-report questionnaires completed in-person on a laptop computer, and 2) EMA completed daily via smartphone (4 random assessments daily, 1 daily dairy, pre-quit smoking assessments, and post-quit urge and lapse assessments). GPS coordinates (i.e., latitude and longitude) will be captured at the time of each EMA assessment. Smoking status will be evaluated at each visit via expired carbon monoxide and in-person interview. Saliva cotinine will be measured via test strips at the final follow-up visit, values will be recorded, and strips will be discarded in a biohazard container. Measurement of height will be collected at the first visit and weight will be collected at each in-person assessment. Attendance will be noted by the research staff each week.
- Recruitment and Informed Consent.** Individuals will be referred from TTRP and recruited using Triafacts. During the first visit, individuals will be provided with detailed information about the study and given the opportunity to have their questions answered within a private room to ensure confidentiality. Written informed consent will be obtained from those who are interested in participating. A certificate of confidentiality will be obtained.
- Risks.** Participation in this study poses minimal risk to participants. However, one potential, although unlikely, risk to participants is loss of confidentiality. The severity of harm in the case of loss of confidentiality may range from mild to severe depending upon the individual and the specific circumstances. However, the risks of participation in the study are similar to that of participation in standard care, as loss of confidentiality may be experienced in either case. The investigators are unaware of any risks associated with the use of the Vitalograph BreathCO monitor for the measurement of expired carbon monoxide levels.
- Protections against Risk.**

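### Does the week-26 primary endpoint need a written coding rule for non-attenders who return only a mailed cotinine kit?

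*Combined protocol and SAP*

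**What the plan says.** The Abstract makes biochemically verified 7-day point prevalence abstinence at 26 weeks the primary outcome and names no test.

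- **CO.** Under Measures in Section D, abstinence "will be verified with a CO level of < 10 on the quit day, and ≤ 6 ppm at all subsequent post-quit visits". Section G (Sources of Research Material) agrees: "Smoking status will be evaluated at each visit via expired carbon monoxide and in-person interview".
- **Cotinine.** It is collected only at week 26. The visit text gives its role: "Saliva cotinine will also be measured via NicAlert test strips to provide additional evidence of abstinence". Measures supplies the cut-off: "Cotinine levels of < 10 ng/ml suggest abstinence from smoking".
- **Remote visits.** The COVID-19 paragraph in Section D has participants "provide a smartphone-based CO measurement using a Smokerlyzer iCO monitor", so a remote visit yields a CO value.
- **Week-26 non-attenders.** The Visit 9 text in Section D reads: "Participants who do not attend will be contacted by phone to obtain their self-reported smoking status and mailed a saliva cotinine test". Non-attenders on the quit day and at weeks 4, 8 and 12 are only phoned.
- **Analysis.** Section E, Aim 1, "assumes a 30% drop-out rate for both treatment arms" and states that "participants with missing data or who have dropped out of treatment will be considered non-abstinent". A completer analysis leaves out anyone without complete smoking status data.

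**The concern.** Take a participant who completes neither an in-person nor a remote week-26 visit, reports 7-day abstinence by phone, and returns a kit below 10 ng/ml. Two codings seem available.

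- **Non-abstinent.** Verification is by CO, there is no CO, and missing data count as smoking.
- **Abstinent.** Cotinine is a listed week-26 biological measure with a cut-off, it was mailed to this person, and the result is negative.

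No sentence chooses between them, and the completer analysis inherits the question because complete smoking status is not defined. The same data could then give two primary abstinence counts. If kit return differed by arm, the choice could move the odds ratio in either direction, and an analyst who chose after seeing the arms compared could favour one answer. How to classify a positive kit from someone using nicotine replacement is also unstated.

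**Working it through.** **1. What the text covers.** Both CO sentences are tied to visits. A person who is phoned and mailed a kit has made no visit, so neither sentence strictly reaches them. The non-abstinent reading also requires calling data missing when a self-report and a biochemical result are both in hand. The kit is added to the phone call at one time point only, the primary one, and has a numerical cut-off. If it could never verify, it would have no evident role in the primary outcome. The abstinent reading is therefore the better supported, though not stated outright.

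**2. How many people.** Section E gives 160 per arm and 30% drop-out: 0.70 × 160 = 112 completers, which is the plan's figure, and 0.30 × 160 = 48 others. The 48 is a ceiling. It treats every drop-out as a reachable non-attender, and it includes people who complete a remote CO visit or whom Section E already codes as non-abstinent for leaving treatment. The documents give no kit-return rate.

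**3. Baseline with CO only.** Section E ties 10% (standard care, SC) and 22% (contingency management, CM) to the 112 completers.

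- Abstainers: 112 × 0.10 = 11.2 and 112 × 0.22 = 24.64.
- Out of 160: 7.0% and 15.4%.
- Odds ratio: (0.154/0.846)/(0.070/0.930) = 2.42.
- Two-sided power at 0.05: Φ{[|p₂−p₁|√n − 1.96√(2p̄(1−p̄))]/√(p₁(1−p₁)+p₂(1−p₂))} with n = 160 and p̄ = 0.112. This is Φ[(1.0625 − 0.8742)/0.4420] = 0.665.

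The 0.665 comes mainly from applying missing-equals-smoking to rates set for completers. That is a separate matter from the kit.

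**4. Counting kits.** Let r be the assumed share of the 48 returning a kit, and q the assumed abstinence rate among them. Each arm gains 48 × r × q abstainers.

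| Assumption | r | Added SC / CM | Rates SC / CM | OR | Power |
|---|---|---|---|---|---|
| q = 10% / 22% | 10% | 0.5 / 1.1 | 7.3% / 16.1% | 2.43 | 0.686 |
| | 25% | 1.2 / 2.6 | 7.75% / 17.05% | 2.45 | 0.716 |
| | 50% | 2.4 / 5.3 | 8.5% / 18.7% | 2.48 | 0.761 |
| q = 5% / 11% | 10% | 0.2 / 0.5 | 7.15% / 15.7% | 2.42 | 0.676 |
| | 25% | 0.6 / 1.3 | 7.4% / 16.2% | 2.43 | 0.691 |
| | 50% | 1.2 / 2.6 | 7.75% / 17.05% | 2.45 | 0.716 |
| q = 16% in both arms | 10% | 0.8 / 0.8 | 7.5% / 15.9% | 2.33 | 0.649 |
| | 25% | 1.9 / 1.9 | 8.2% / 16.6% | 2.23 | 0.626 |
| | 50% | 3.8 / 3.8 | 9.4% / 17.8% | 2.09 | 0.592 |

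With q at 10% / 22% and unequal return, SC 25% and CM 50% gives OR 2.74; SC 50% and CM 25% gives 2.21.

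**5. Positive kits in nicotine users.** That replacement nicotine raises cotinine is not in the documents. Assuming 50% return and 30% use, the numbers are 48 × 0.5 × 0.10 × 0.3 = 0.7 in SC and 48 × 0.5 × 0.22 × 0.3 = 1.6 in CM.

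**The case for a change.** The strongest case is that few people are needed to change the result. With 11 and 25 abstainers of 160, the uncorrected chi-square gives p = 0.013. Adding 4 SC and 1 CM kit-verified abstainers (15 against 26) gives p = 0.066; adding 8 and 5 (19 against 30) gives p = 0.088. Since return could differ by arm, a careful plan would name the rule before the arms are compared, and one sentence would do it.

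The arithmetic is right, and it stands that no sentence states the rule. But both examples need more kit-verified abstainers in SC than in CM, against the direction of the planned effect. The second needs at least 8/48 = 17% of SC non-attenders to return a kit and be abstinent, when the plan expects 10% abstinent among SC completers. Counts running the other way strengthen the result: adding 5 and 11 (16 against 36) gives p = 0.002. The examples show that borderline results are sensitive to a few recoded people; they do not show that either coding is biased.

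It can also be said that CO alone gives a cleaner, single-test endpoint. That is a fair preference, but it discards a biochemical result the plan goes out of its way to collect. Choosing between one test and more complete verification is a trade-off.

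**Conclusion.** No change follows. The plan leaves one small group uncoded in terms, but its wording favours treating a negative mailed kit as verification, and the conservative alternative is also sound. A competent analyst would settle on one and report it. With equal kit return and the planned abstinence ratio between arms (10% to 22%, or half of each), the odds ratio stays between 2.42 and 2.48 for up to 50% return. The wider range, 2.09 to 2.74, comes from assuming equal abstinence in both arms or a twofold difference in return, and its direction is unknown. All these figures assume the full drop-out allowance of 48 per arm is mailed kits, which is an upper bound; the true number is not given. A special rule for nicotine users would rest on pharmacology outside the documents, for about 0.7 and 1.6 people under the stated assumptions. For attenders, in clinic or remote, the text already makes CO the verifier and cotinine supporting evidence.

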Quit Day (Visit 2). Participants will complete self-report questionnaires on a laptop computer; and expired CO and weight will be measured in a private room to ensure confidentiality. All participants will be paid \$30 for the completion of the in-person assessments at visit 2, which take approximately 40 minutes to complete. Participants randomized to the CM treatment will receive an additional \$20 payment if they self-report abstinence from smoking since 10 p.m. the prior evening, and their expired is CO level is < 10 ppm (please note that the less stringent cut-off of 10 ppm will be used to verify abstinence at the first visit only, due to the recency of quitting). Participants who do not attend will be contacted by phone to obtain their self-reported smoking status.

1 Week Post-Quit (Visit 3). Participants will complete self-report questionnaires on a laptop computer; and expired carbon monoxide (CO) and weight will be measured in a private room to ensure confidentiality. In addition, participants will receive \$30 for the completion of the in-person assessment at visit 3, which takes approximately 30 minutes to complete. Participants randomized to the CM treatment will receive an additional \$25 payment if they self-report continuous abstinence from smoking since the quit day and have an expired CO level of ≤ 6 ppm. **2 Weeks Post-Quit (Visit 4).** Expired carbon monoxide (CO) and weight will be measured in a private room to ensure confidentiality. Participants will receive \$30 in gift cards for the completion of the assessment, which will take approximately 5 minutes to complete. Participants randomized to the CM treatment will receive \$30 payment if they self-report continuous abstinence from smoking since the quit date and have an expired CO level of ≤ 6 ppm. **3 Weeks Post-Quit (Visit 5).** Expired carbon monoxide (CO) and weight will be measured in a private room to ensure confidentiality. Participants will receive \$30 in gift cards for the completion of the assessment, which will take approximately 5 minutes to complete.

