Participants randomized to the CM treatment will receive \$35 payment if they self-report continuous abstinence from smoking since the quit date and have an expired CO level of ≤ 6 ppm. **4 Weeks Post-Quit (Visit 6).** Participants will complete self-report questionnaires on a laptop computer; and expired CO and weight will be measured in a private room to ensure confidentiality. Participants will receive a \$30 payment for completion of the in-person assessments, which will take approximately 50 minutes to complete. Upon return of the smartphones, participants will be compensated based on the percentage of completed random assessments. Specifically, those who complete 50%-74% of assessments will receive \$75 in gift cards, those who complete 75%-89% of assessments will receive \$100 in gift cards, and those who complete 90% or more of their assessments will receive \$150 in gift cards. Participants who do not attend will be contacted by phone and/or mail to request that the phone be returned by mail (postage paid envelopes will be sent) or in-person at the next visit. When participants return the phone they will be compensated according to the compensation schedule described above. Participants whose only form of telephone contact is the study phone will be

allowed to keep and use the study phone for their remaining duration of the study (up to their 26-week post-quit visit). These participants will still be compensated for EMA completion on the same schedule as any other participant and they will be asked to complete the same number of EMA assessments as any other participant. Participants randomized to the CM treatment will receive an additional \$40 payment if they self-report continuous abstinence from smoking since the quit date and have an expired CO level of ≤ 6 ppm. Participants who do not attend will be contacted by phone to obtain their self-reported smoking status.

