Hardware. The Samsung Galaxy Exhibit smart phone uses the Android 4.1 Jellybean operating system. The phone has a 3.8 inch (480x800 pixel resolution) touch screen display, a built in microphone, earphone jack, audio speaker, and a rechargeable battery with 9.0 hours of talk time. It is Wi-Fi and GPS capable. Participants navigate through the EMA program and enter data simply by touching the screen, similar to a pen-and-paper questionnaire. Thus, computer/typing skills are not required. Participants have the ability to call (e.g., if they have problems completing EMAs) and receive calls from research staff through the smart phone free of charge. The smart phones are equipped with a Secure Digital card to store data as it is collected.

Programming. The EMA program will be developed by and accessed through the mHealth core led by [name] (co-investigator). The core is located in the TSET Health Promotion Research Center and is part of the Stephenson Cancer Center. The EMA program that was developed for the PREVAIL pilot study will be modified for the purposes of the proposed study.

EMA Assessment Types. Three types of assessments will be used: daily diary, random sampling, and event sampling (i.e., pre-cessation smoking, urge, post-cessation lapse). Daily diary assessments will be completed once every day (30 minutes after waking), and all questions will refer to the previous 24 hours. Random sampling and daily diary assessments will be initiated by the smart phone. The phone will audibly and visually cue each random assessment for 30 seconds. If the participant has not responded after three prompts, the assessment will be recorded as missed. Random sampling will include four smart phone initiated assessments per day, scheduled to occur during each participant's normal waking hours. Event sampling is initiated by participants. Participants are instructed to complete "smoking assessments" when they smoke prior to the quit date, "urge assessments" when they have an urge to smoke or they feel like they almost smoked, and "lapse assessments" if they smoke after the quit date. GPS coordinates (i.e., latitude and longitude) will be collected via the smartphone during each assessment. On average, random and event sampling assessments will take 2.5 minutes to complete, while daily diary assessments will take approximately 5 minutes to complete. All assessments will be date and time stamped for future analyses.

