week), participants will be instructed to click the “record cigarette” button immediately prior to smoking each cigarette. Because the assessment burden would be excessive for heavy smokers if each smoking occasion were assessed, two of these smoking occasions each day will be randomly sampled for pre- and post-cigarette assessments. Ten minutes after completing the pre-cigarette assessment, the smartphone will automatically prompt the post-cigarette assessment which includes unique items and the core EMA items. Urge Assessments. Following their quit date, participants will be instructed to initiate an urge assessment each time they “experience an urge to smoke” and answers should be focused on their immediate thoughts/feelings. Lapse Assessments. Participants will be instructed to complete lapse assessments each time they smoke after the quit date. Questions asked during lapse assessments are nearly identical to those presented in random and urge assessments. However, questions are worded to separately assess the participant’s responses immediately prior to AND following the lapse. Post lapse assessments also query about recent discrimination, the reinforcing value of the lapse cigarette(s), and lapse causes.

E. Statistical Methods

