Note: All detectable effects are presented in standard deviation units and are at 80% power.

include treatment group, age, gender, race/ethnicity, nicotine dependence, and pharmacological treatment. **Generalized Linear Mixed Models.** Smoking cessation assessment data and EMA data will be measured repeatedly and are therefore correlated within subjects. Thus, our analytic approach will include generalized linear mixed model regression analysis (GLMM). GLMM is a flexible analytic approach with wide use in health sciences research. GLMM can handle fixed and random effect model parameters, nested designs, and repeated measures with various correlation structures. GLMM can also handle normal and non-normal outcomes such as dichotomous smoking status variables, different variance functions, as well as unbalanced designs where the number of repeated observations varies across individuals. EMAs create an enormous amount of data. For instance, in the 2 weeks that PREVAIL participants carried the EMA device, we collected over 70 assessments per participant. This rich data will allow us to address multiple within and between subjects questions in this understudied and vulnerable group of low SES smokers. For example, we will examine key EMA variables (e.g., negative affect, smoking urge, stress) and variable parameters (e.g., intercept, slope, quadratic term, volatility) as potential predictors of week 26 smoking abstinence. In addition, we will identify key EMA variable parameters that predict specific lapse episodes (e.g., the first lapse following the quit date). This information may be used to detect high risk for relapse situations that may be targeted in future “smart interventions.” EMA data will also allow us to address other important participant specific (i.e., within subjects) questions like: 1) what psychosocial changes occur as an individual progresses from lapse to relapse, and 2) what impact specific episodic events like exposure to stressors (e.g., discrimination events, acute urges) have on cessation self-efficacy and mood and the impact on smoking lapse.

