General Procedures. Each participant will be assigned an identification number that will be utilized in place of names in all electronic and print data files. The file containing the links between participant names and identifiers will be kept in a separate password-protected file, which will be destroyed 12 months after the completion of the study. All print information, including informed consent, questionnaires will be stored in locked filing cabinets at the TSET Health Promotion Research Center. Electronic data (with names omitted) will be maintained on the investigators' computers, and all computers and electronic files will be password protected. Participants will complete smartphone assessments through an encrypted mobile application, and all data is automatically saved and sent to institutional servers in real-time. Anthropometric measures, CO, and saliva cotinine will be collected in a private room. All project staff will receive training focused on each of the following topics: 1) project rationale and objectives, 2) the informed consent process, 3) general data collection procedures (e.g., computer data collection, privacy), 4) measurement of anthropometric data, 5) use of the carbon monoxide ecolyzer, and 6) saliva cotinine measurement via test strips. A certificate of confidentiality will be obtained.

EMA Confidentiality Procedures. The following features are designed to address smartphone/EMA/GPS data security issues: 1) the data stored on the smartphone device is in a SQLite database in a sandbox environment where read/write operations are only available through the programming application. No file or output is readable to end users, 2) a password (only known to researchers) is required to authenticate the current user before data can be downloaded from the smartphone device to the server, 3) the web browser application linking the principal investigator's computer to the database is on HTTPS protocol (SSL certificate with encryption) which will guarantee the data transfer from web browser to the backend database is well protected, and 5) the backend database is hosted by the University of Oklahoma Data Center in a secure setup.

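### CM participants, unlike SC participants, have a financial reason not to log lapses on the study phone, so Aim 2 lapse data may be under-reported more in CM

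*Combined protocol and SAP*

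**What the plan says.** **Lapse logging, both arms.** Section D (Event Sampling, Lapse Assessments): "Participants will be instructed to complete lapse assessments each time they smoke after the quit date". Section D (EMA Assessment Types) adds that "Event sampling is initiated by participants", so the phone does not prompt a lapse entry. The daily diary, which the phone does prompt, asks how many cigarettes were smoked the day before. Both run from one week before the quit date to three weeks after it, and entries are date- and time-stamped.

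**Payment for abstinence, CM only.** The quit-day payment is an "additional \$20 payment if they self-report abstinence from smoking since 10 p.m. the prior evening", with CO below 10 ppm. Week 1 brings an "additional \$25 payment if they self-report continuous abstinence from smoking since the quit day", with CO of 6 ppm or less. At weeks 2, 3 and 4 the payments of $30, $35 and $40 are made "if they self-report continuous abstinence from smoking since the quit date and have an expired CO level of ≤ 6 ppm". At weeks 8 and 12 the payments are $50 each and need only seven days of abstinence.

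**Payment for phone assessments, both arms.** Under 4 Weeks Post-Quit (Visit 6), "participants will be compensated based on the percentage of completed random assessments". Lapse and diary entries do not count.

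**Data flow.** Section G (Protections against Risk, General Procedures) says of the smartphone assessments that "all data is automatically saved and sent to institutional servers in real-time".

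**Use of the lapse data.** Section E (Generalized Linear Mixed Models) says that "we will identify key EMA variable parameters that predict specific lapse episodes (e.g., the first lapse following the quit date". It also plans to study what changes as a person moves from lapse to relapse.

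**The concern.** A CM participant who smokes once between visits and intends to claim the next payment has a reason not to leave a phone record of it. An SC participant in the same position loses no money by logging the cigarette. The recording of an Aim 2 outcome may thus depend on treatment arm.

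Misclassification that differs by arm matters for the lapse models. If lapses are missed more often in CM, the associations of mood, urge and stress with lapse are estimated there from an incomplete set of events, and the missing events are probably not a random subset. Treatment group as a main-effect covariate absorbs a difference in the overall level of recorded lapses. It does not repair predictor-lapse associations that are distorted in one arm.

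CO does not recover the lost events. It is measured at visits, and Section D (Measures) describes it as a marker of recent smoking. It cannot date a lapse, and a brief lapse days before a visit need not show.

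The visible text neither keeps phone entries from the staff who decide payment nor plans a check for reporting that differs by arm.

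**Working it through.** **Step 1. Reproduce the plan's total.** Section C gives $150 as the most a pilot CM participant could earn from the quit day through week 4. Section D uses the same five amounts:

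20 + 25 + 30 + 35 + 40 = $150. This agrees.

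Adding weeks 8 and 12 gives 150 + 50 + 50 = $250 in abstinence payments for the current trial.

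**Step 2. Payments that depend on unbroken abstinence.** These are weeks 1 to 4: $25, $30, $35 and $40. The quit-day $20 is left out because it is settled before any lapse that follows that visit. The $100 at weeks 8 and 12 is left out because an early lapse does not rule it out.

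**Step 3. Amount still open at a first lapse.** This is the sum of all later payments that require unbroken abstinence.

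| First lapse occurs | Sum | CM | SC | In phone-assessment window? |
|---|---|---|---|---|
| Between quit day and week 1 visit | 25 + 30 + 35 + 40 | $130 | $0 | Yes |
| Between week 1 and week 2 visits | 30 + 35 + 40 | $105 | $0 | Yes |
| Between week 2 and week 3 visits | 35 + 40 | $75 | $0 | Yes |
| Between week 3 and week 4 visits | 40 | $40 | $0 | No |

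The largest figure is 130/150 = 87% of what can be earned through week 4 and 130/250 = 52% of all abstinence payments. Each figure is a ceiling: it assumes that the participant attends every remaining visit through week 4 and meets the CO limit at each.

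**Step 4. Reward for logging a lapse.** It is $0 in both arms, because phone-assessment pay counts random prompts only. Failure to log can therefore occur in either arm. What differs is the money at risk: $75 to $130 in CM during the window, and nothing in SC.

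**Step 5. Which analyses are exposed.** Section A words Aim 2 as concerning intervention participants. Section E bases the Aim 2 detectable effects on all 320 participants and lists treatment group as a possible covariate. If the arms are pooled, the outcome may be misclassified differently by arm. If CM alone is analysed, every lapse record comes from the arm with the motive to withhold.

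**Step 6. What cannot be computed.** The documents give no rate of concealed lapses in either arm, so the bias has no estimate.

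**The case against.** **A phone entry does not cost anyone a payment.** A reader might infer that logging a lapse forfeits up to $130. The documents do not say so. Section D ties payment to visit self-report and CO. Section G has smoking status assessed by CO and interview at visits, and Section H expects disputes when self-report conflicts with biochemical verification, without mentioning phone data. Data reaching a server does not show that the staff who decide payment see it. This objection stands: the mechanism is indirect and works through the record a participant is willing to leave.

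**Under-reporting need not be confined to CM.** That inference is also tempting, but lapse entries are voluntary and unpaid in both arms. Only the added motive is specific to CM.

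**The motive is narrow.** Someone who fails the CO test loses that payment whatever was logged, and someone who has already admitted smoking has nothing left to protect through week 4. The motive is strongest for brief lapses that CO misses. This limits the likely effect, more for the lapse-to-relapse path than for first lapse.

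**No comparison of time to lapse between arms is planned.** A reader might expect the bias to appear as a false delay of lapse in CM. Section E plans predictors of lapse and within-person questions, and it compares cessation between arms at study visits, so that harm does not arise from the stated plan.

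**The phone-assessment pay rule is the same in both arms.** Paying for random prompts alone cannot create a difference between arms. Nor would paying for the diary remove one, since a paid diary can still record zero cigarettes.

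**What participants are told cannot be checked.** Consent pages were removed and the payment schedule in Table 1 is not in the available text. An explanation may already exist there.

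**Conclusion.** The point holds in a limited form. During the three post-quit weeks of phone assessment, CM participants have a financial motive, absent in SC, not to log lapses. At most $130, $105 or $75 is at stake, depending on the week of the first lapse. Lapse entries may therefore be under-reported more in CM than in SC, which could distort the Aim 2 models of first lapse and of progression to relapse.

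This rests on two assumptions: that some participants who deny a lapse at a visit also avoid recording it on the phone, and that no assurance to the contrary is given in the consent text or Table 1. The first is a reasonable inference, not a shown result, and the extent is unknown.

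The primary outcome is untouched, because abstinence at week 26 is biochemically verified and carries no abstinence payment. The affected analyses are secondary, so severity is minor.

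**What to change.** 1. **Conduct.** State in Sections D and G that diary and lapse entries are not visible to staff who decide payment and are never used for it. Tell every participant in both arms so during the visit 1 phone training, unless the consent text already does. Payment amounts and abstinence criteria stay as they are. The cost is a script line and an access restriction on the server. The downside is that a participant may be paid despite a logged lapse. Because unlogged lapses cannot be recovered, this helps only participants who have not yet begun phone assessment.

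2. **Analysis.** Add three items to Section E:
   - Compare phone-recorded lapses with visit self-report and CO, by arm, over weeks 1 to 3. Agreement with self-report is weak evidence in CM, because both carry the same motive. A visit CO above 6 ppm with no logged lapse since the previous visit is more informative, but it misses the brief lapses of most concern.
   - Include a treatment-by-predictor term in the lapse models that use both arms. Such a term may reflect a real difference between arms as well as a reporting one, so read it together with the first item.
   - Repeat the lapse models in SC alone as a sensitivity analysis. The cost is precision, since SC has half the sample (160 of 320).

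Section E should also say whether the lapse models use both arms or CM only. These items need no new data and can be adopted at any time before the lapse analyses.
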